2.3 Sample Size

Based on preliminary U.S. IDE data, we estimate the standard deviation to be 1.62. Based on the above formula for calculating tolerance intervals, a sample size of 60 will allow us to claim that 70% of the alignments fall within $+\/- 2$ degrees. The sample size formula plans for $+\/- 2$ degrees to account for the initial IDE data showing the average offset is about -1 degrees and our goal is to show that 70% or more are within $+\/- 3$ degrees. To account for loss to follow up and patient dropouts, enrolling 70 patients includes a 10% loss to follow-up to ensure there are 60 patients at the end of the study.

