2.2 Data Analysis

Data will be analyzed using SAS 9.4 or higher. The Type I error rate for the primary study analysis will be 0.05. Comparisons for secondary, exploratory, and safety analyses will be two-sided comparisons using $\alpha = 0.05$, with no adjustment for multiple comparisons.

Primary Analysis: The primary analysis will be conducted on the as-treated data set. In the as-treated-analysis for the primary endpoint, missing data will be treated as described in Section 1.1.

The primary endpoint is to show achievement of mechanical leg alignment in HKA frontal plane (± 3 degrees) with X-PSI Knee System is as accurate as with standard instrumentation at 4-6 weeks post operation. The X-PSI Knee System cohort will be compared with current literature (70% of cases within ± 3 degrees).

To determine the upper and lower limits with 95% confidence that 70% of the X-PSI patients' HKA frontal plane measurements are contained, a 70% tolerance interval will be constructed based on the mean and standard deviation of the HKA frontal plane measurements from patients in the study. A tolerance interval is defined as "a statistical interval within which, with some confidence level, a specified proportion of a sampled population falls". In this study, we will claim with 95% confidence that 70% of the X-PSI patients fall within a computed tolerance interval. This method allows us to state an upper and lower limit in which we can claim 70% of the alignments will fall within with a given confidence (95%).

The upper and lower tolerance limits are defined as

$$Y_L = \bar{Y} - K \cdot s; \quad Y_U = \bar{Y} + K \cdot s;$$

where Y_L and Y_U are the lower and upper tolerance limits respectively, \bar{Y} is the sample mean, s is the sample standard deviation and k is defined as

$$K = \sqrt{\frac{v\left(1 + \frac{1}{N}\right)z_{(1-p)/2}^2}{X_{1-y,v}^2}}$$

where p is the percentage (proportion) of the population we want to claim within the interval, $X_{1-y,v}^2$ is the critical value of the chi-square distribution with degrees of freedom v that is exceeded with probability y , and $z_{(1-p)/2}$ is the critical value of the normal distribution associated with cumulative probability $(1-p)/2$.

For this study, $p = 0.7$ (70%), and $y = 0.95$ (95%). The study will be considered a success if both the upper and lower tolerance limits are within $+\/- 3$ degrees.

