2.4 Study Report

The primary analysis will be performed after all patients reach the 4-6 weeks follow up time point. Data will be analysed using the methods described in Section 1.2.

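### Section 2.3 presents 60 patients as enough to support the accuracy claim, but at the planning values the chance of meeting the ±3° success rule is only 52% to 56%, and the plan does not say so

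*Combined protocol and SAP*

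**What the plan says.** Section 2.3 (Sample Size) of the combined protocol and SAP takes two planning values from preliminary IDE data. The first is the spread: "we estimate the standard deviation to be 1.62" degrees. The second is a mean offset of about -1°. From the tolerance interval formula it concludes that "a sample size of 60 will allow us to claim that 70% of the alignments fall within" ±2 degrees. It explains the choice of ±2° by "initial IDE data showing the average offset is about -1 degrees and our goal is to show that 70% or more are within" ±3 degrees. On attrition it says that "enrolling 70 patients includes a 10% loss to follow-up to ensure there are 60 patients at the end of the study".

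Section 2.2 (Data Analysis) sets the interval at 70% content with 95% confidence and gives the decision rule: "The study will be considered a success if both the upper and lower tolerance limits are within" ±3 degrees.

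No section gives a power or a probability of meeting this rule.

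**The concern.** The sample size is chosen so that a half-width of 2° added to an offset of 1° reaches the 3° limit. That places the planned lower tolerance limit on the success boundary and treats the sample mean and SD as if they were known in advance. Both will vary from sample to sample, and a limit centred on its boundary falls on the wrong side about half the time. The 95% in section 2.2 does not cover this. It is the confidence of the tolerance statement, which guards against a false claim and says nothing about how often a good device will pass.

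A sponsor, ethics committee or investigator reading section 2.3 would expect 60 cases to be sufficient if the device performs as in the IDE data. They could not see that there is no margin for sampling variation, or how strongly the result depends on an offset given only approximately. They would also be poorly placed to interpret a miss.

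**Working it through.** **Inputs.** SD 1.62°, offset -1°, N = 60 evaluable, 70 enrolled, 10% loss (section 2.3). Content p = 0.70, confidence 0.95, limits ±3° (section 2.2). Assumptions: normally distributed alignments, as the formula implies, and v = N - 1. The plan does not define v further; this choice reproduces its N.

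**Step 1: reproduce N = 60.** K = √[v(1 + 1/N)z² / χ²], with z = 1.0364 (z² = 1.0742) and χ² the lower 5% point on v degrees of freedom.

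- N = 59: K = 1.2357; K × 1.62 = 2.002°.
- N = 60: χ² on 59 df = 42.34; K = √(59 × 1.01667 × 1.0742 / 42.34) = 1.2336; K × 1.62 = 1.998°.

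So 60 is the smallest N with a half-width of at most 2°. The arithmetic in section 2.3 is right.

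**Step 2: place the interval against the rule.** At N = 60 the planned limits are -1 - 1.9985 = -2.9985° and -1 + 1.9985 = +0.9985°. The room at the lower end is 0.0015°. The standard error of the mean alone is 1.62/√60 = 0.209°.

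**Step 3: probability of success.** Success requires Ȳ - K·s ≥ -3 and Ȳ + K·s ≤ 3, where Ȳ ~ N(-1, 1.62²/N) and, independently, (N - 1)s²/1.62² ~ χ² on N - 1 df. For a given s the probability is

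Φ[(3 - K·s + 1)/(1.62/√N)] - Φ[(-3 + K·s + 1)/(1.62/√N)],

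set to zero if K·s > 3, and then averaged over the distribution of s.

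| Evaluable N | K | Planned lower limit | P(success), integration | Simulation (2,000,000 draws) |
|---|---|---|---|---|
| 60 | 1.2336 | -2.998° | 0.516 | 0.517 |
| 63 (70 less 10%) | 1.2277 | -2.989° | 0.530 | 0.530 |
| 70 | 1.2156 | -2.969° | 0.560 | 0.560 |

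The upper limit never failed in the simulation; the lower limit decides the result.

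*Hand check at N = 60.* E(s) = 0.9958 × 1.62 = 1.613, so the expected lower limit is -1 - 1.2336 × 1.613 = -2.990. Its standard deviation is about √[1.62²/60 + 1.2336² × 1.62²/(2 × 59)] = 0.279. Then Φ(0.010/0.279) = Φ(0.036) ≈ 0.51, in agreement.

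**Step 4: what the rule means at these values.** The true proportion within ±3° at mean -1°, SD 1.62° is Φ(4/1.62) - Φ(-2/1.62) = 0.885. If the true proportion were exactly 70%, the rule at N = 60 would pass with probability 0.010 (mean 0°, SD 2.895°) or 0.002 (mean -1°, SD 2.709°).

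**Step 5: sensitivity.** The documents give no uncertainty for the offset or SD, so these values are illustrative. Offsets from -0.5° to -1.5° are what a figure of about -1 would cover if rounded to a whole degree.

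| Offset | SD | N = 60 | N = 70 |
|---|---|---|---|
| -0.5° | 1.62° | 97% | 98% |
| -0.9° | 1.62° | 66% | 71% |
| -1.1° | 1.62° | 37% | 41% |
| -1.5° | 1.62° | 4% | 3% |
| -1° | 1.50° | 73% | 78% |
| -1° | 1.75° | 31% | 33% |

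For scale only: at offset -1° and SD 1.62° the rule reaches 80% at 154 evaluable cases (0.8015) and 90% at 226 (0.9002).

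**The case against.** The strongest reply is that the sentence in section 2.3 is a precision statement about a ±2° width. Read that way, 60 is correct and the wording is ordinary planning language, not a guarantee. This does not rescue it. The same section names ±3° as the goal and uses the offset to get there. Even on the narrow reading, the observed half-width is at most 2° in only about 53% of samples at N = 60 and 59% at N = 70.

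A second reply is that 60 is the pessimistic case. Seventy are enrolled, the 60 are those remaining at the end of the study, and section 2.4 says "The primary analysis will be performed after all patients reach the 4-6 weeks follow up time point", when fewer will have been lost. This is fair: 63 to 70 evaluable cases is the more realistic range. It moves the figure only to 53% to 56%.

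A third is that 52% is one point on a steep curve and should not be read as the study's actual chance of success. That stands, and it is a reason to report the sensitivity as well.

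Finally, the rule is conservative and this is a single-arm post-market study, so no misleading positive claim follows. That also stands. It limits the consequence to an inconclusive result but does not make the sample-size statement correct.

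**Conclusion.** The concern holds. The calculation of N = 60 is correct, but section 2.3 attributes to that number a property it does not have. If the planning values are exactly true, the study meets its own success rule with probability of about 52% at 60 evaluable cases and 53% to 56% at 63 to 70. It would therefore miss the rule almost half the time, although true coverage of ±3° would be about 88.5%. These figures rest on normal data, v = N - 1, offset -1° and SD 1.62°. Small departures from the last two move the result a great deal. This should be fixed. The attrition allowance is not the problem: 60/0.9 rounds up to 67, so 70 enrolled is enough for 60 evaluable.

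**What to change.** In section 2.3, replace the sentence that says what 60 patients will support with text such as:

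> At SD 1.62° the expected half-width of the tolerance interval with 60 evaluable cases is about 2°. With a mean offset of -1° the probability that both limits lie within ±3° is about 52% with 60 evaluable cases and 53% to 56% with 63 to 70. This is sensitive to the assumptions: with 60 cases and SD 1.62° it is about 97% at an offset of -0.5°, 66% at -0.9°, 37% at -1.1° and 4% at -1.5°; at offset -1° it is about 73% for SD 1.50° and 31% for SD 1.75°.

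If the sponsor can state the uncertainty of the IDE mean and SD, that range should replace the illustrative one, and the last sentence can then be shorter.

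The cost is a few sentences and a less favourable stated figure. No patients are added, and N, the analysis and the success rule in section 2.2 stay as they are. The change does not raise the chance of success; it only states it.

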2.4 Study Report

The primary analysis will be performed after all patients reach the 4-6 weeks follow up time point. Data will be analysed using the methods described in Section 1.2.
